8.0 Research Plan and Procedures

8.1 HYPOTHESIS: Describe the hypothesis or what the study hopes to prove:

Our Hypotheses are:

1. Targeted Intermittent Oral Naltrexone (ION) will significantly reduce meth use, as determined by the proportion of meth-positive urine tests, compared to placebo.
2. Targeted ION will significantly reduce meth-associated sexual risk behavior, as determined by the audio computer assisted self-interview (ACASI) data and sexual risk behavior data, compared to placebo.
3. Targeted ION will significantly increase PrEP adherence among HIV-negative participants and ART adherence among participants living with HIV, as determined by drug levels and viral load testing; and sexual risk behavior data accounting for PrEP use and viral suppression, compared to placebo.

8.2 AIMS: List the specific aims:

Our Aims are:

1. To determine the efficacy of ION vs. placebo in reducing meth use, as determined by the proportion of meth-positive urine tests
2. To determine the efficacy of ION vs. placebo in reducing meth-associated sexual risk behaviors
3. To determine the efficacy of ION vs. placebo in increasing PrEP adherence among HIV-negative participants and ART adherence among participants living with HIV

8.3 DESIGN: Briefly describe the study design (e.g., observational, interventional, randomized, placebo-controlled, blinded, cross-over, cross-sectional, longitudinal, pharmacokinetic, etc.):

Research Design: This is a double-blind, placebo-controlled phase 2b trial in which 60 MSM who use meth will be randomly assigned (2:1) to receive 12 weeks of as-needed intermittent oral naltrexone 50 mg enhanced with an EMA-informed EMI platform, or receive as-needed placebo with EMA-informed EMI. The 12-week treatment period is consistent with other pharmacotherapy

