
TABLE 1: RELEVANT STUDIES BY RESEARCH TEAM

PHARMACOTHERAPY FOR MSM WHO USE SUBSTANCES	(n)	Duration	Retention	# Screened
				(Enroll. ratio)
Harness Study (Intermittent Oral Kudzu)	120	12 weeks	Ongoing	Ongoing

Curb the Line (Lorcaserin)	22	12 weeks	86%	56 (40%)
Say When (Intermittent Oral Naltrexone)	120	12 weeks	89%	269 (45%)
Trex Study (Intramuscular Naltrexone) ¹⁴⁴	100	12 weeks	90%	194 (52%)
Project iN (Intermittent Oral Naltrexone ¹⁰⁹)	30	8 weeks	95%	49 (61%)*
BUMP Study 1 (Bupropion ¹²⁴)	30	12 weeks	90%	54 (56%)
BUMP Study 2 (Mirtazapine ⁶⁶)	60	12 weeks	95%	212 (56%)
BUMP Study 3 (Aripiprazole ¹²⁵)	90	12 weeks	83%	375 (24%)
M 2.0 Study (Mirtazapine)	120	48 weeks	94%	241 (50%)
Observational/Ecologic Momentary Studies on Substance Use		(n)	Duration	
SUPreMe Study (Substance Use and PrEP among MSM)		250	1 year	
Digital Divide Ecological Momentary Study ¹¹⁸		45	7 days	
SAMBA: Stimulants Alcohol Momentary Behavioral Assessments		263	14 days	
Project Youth HIV Risk Estimator Development		66	21 days	
Smart-T EMI Study		59	3 weeks	

8.6 * TREATMENT PROTOCOL: Is this a treatment study, i.e. does this study intend to provide treatment to individuals with a medical or psychological condition: (REQUIRED)

Yes No

8.7 * BILLABLE PROCEDURES: Does this study involve any procedures, lab tests or imaging studies that have a CPT code and could be billable to patients, their insurance, Medi-Cal, Medicare, or any other entity (answer 'Yes' even if the study is going to pay for all the procedures): (REQUIRED)

Yes No

If you are not sure if your study involves billable procedures, send an email to the UCSF Office of Clinical Research (OCR) for help answering this question.

8.8 * COMMON RESEARCH ACTIVITIES: Types of research activities that will be carried out. Check all that apply and describe in more detail in the 'Procedures / Methods' section: (REQUIRED)

- Interviews, questionnaires, surveys
- Educational or cognitive tests
- Focus groups
- Social media-based research activities
- Observation
- Fitness tests or other exertion activities
- Use of mobile health apps or other apps
- Collection of data from wearable tech such as Fitbit, Apple Watch, Garmin, motion actigraphs, etc.)
- Non-invasive imaging or testing (MRI, EEG, pulse oximetry, etc.)
- Imaging procedures or treatment procedures that involve radiation (x-rays, CT scans, CT-guided biopsies, DEXA scans, MUGA or PET scan)
- Administration of contrast agent
- Randomization to one intervention versus another

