Trade Drug Name:	NALTREXONE HYDROCHLORIDE																																																																			
Generic Drug Name:	NALTREXONE HYDROCHLORIDE																																																																			
Investigational Drug Name:																																																																				
Identify the name of the manufacturer or source of investigational drug/biologic:	ReVia																																																																			
Is the drug supplied at no cost?	No																																																																			
Is the Drug FDA Approved:	Yes																																																																			
Is this a new drug or a new use of an already approved drug	Yes																																																																			
Is an IND necessary	No																																																																			
IND Number																																																																				
Who holds the IND:	N/A																																																																			
IND details:																																																																				
If FDA Approved and an IND is not required, Please provide a rationale for exemption:	
This study meets exemption criteria under 21CFR312.2: the investigator is not intending to report the study in support of a new indication or change in advertising; there is no significant increase in risk in this study population and it uses the same dose and route as FDA-approved; the study will comply with IRB and informed consent requirements; and the investigator has no disqualifications. We have submitted the UCSF IND Decision worksheet in other study documents.
																																																																			
Are you currently using this IND in another research project?	No																																																																			
If yes, list the IRB Number(s):																																																																				
Will the investigational pharmacy be dispensing?	No																																																																			
If the source is not a FDA licensed facility, provide details regarding the purity, quality, stability and sterility of the investigational drug/biologic:																																																																				

10.3 * MEDICAL DEVICES: Are you **STUDYING any medical devices, in vitro diagnostics, or assays that are either approved or unapproved:(REQUIRED)**

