11.0 Sample Size and Eligibility Criteria

11.1 ENROLLMENT TARGET: How many people will you enroll:

60

If there are multiple participant groups, indicate how many people will be in each group:

The ION+EMI study will enroll 60 participants in the double-blinded placebo controlled clinical trial where 40 participants will receive Intermittent Oral Naltrexone and 20 participants will receive placebo.

11.3 SAMPLE SIZE JUSTIFICATION: Explain how and why the number of people was chosen. For multi-site studies, this is referring to the number that will be enrolled across all sites:

For the phase 2b clinical trial, a sample size of 60 was selected to provide 80% power in 2-sided tests with a type-I error rate of 5% to detect between a 18-22% reduction of meth use among the ION arm, compared to placebo, in ITT and sub-group analyses. We hypothesized on pharmacologic grounds that oral naltrexone will reach full efficacy against meth use almost immediately; accordingly we expect treatment-control differences to be approximately constant over the 12 weeks of the trial. Based on the prior trial (93% retention), we estimate that 90% of participants will be retained at 12 weeks. Under these assumptions, the minimum detectable effects for our outcomes are calculated as follows:

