We follow the Health Insurance Portability and Accountability Act of 1996 (HIPAA) regulations for the protection of private health information for individuals. All study participants screening or enrolling in our studies must sign the HIPAA Authorization Form (unless a waiver of authorization has been approved by the IRB). The Authorization Form is protocol-specific and must be signed along with the consent form when participants first screen or enroll into a study. Before participants sign the Authorization Form, study staff will explain the purpose of the Authorization Form and answer any of the participants' questions. Participants will receive a signed copy of the Authorization Form. Potential participants who choose not to sign the HIPAA Authorization form will be excluded from study participation.

Ensuring medical or professional intervention for adverse events. The study clinician(s) will review data forms daily to monitor safety during the conduct of the trial. If serious or unexpected AEs occur during the trial, the PI will report these occurrences within the specified time frames to the Data and Safety Monitoring Board (DSMB), IRB, NIH, and the FDA as required. All study materials and protocols will be reviewed and approved by the UCSF IRB prior to their use. AE reporting plans are described in the Data and Safety Monitoring plan in this section.

13.4 RESOURCES: Describe the resources in place to conduct this study in a way that assures protection of the rights and welfare of participants: These resources typically include appropriately trained and qualified personnel (in terms availability, number, expertise and experience), funding, space, equipment, and time to devote to study activities. Depending on the nature of the research study, investigators should consider the proximity or availability of critical resources that may be essential to the safety and welfare of participants, such as

- the proximity of an emergency facility for care of participant injury
- availability of psychological support after participation
- resources for participant communication, such as language translation services

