Study staff will assess participants for any medical or psychiatric side effects by asking the participant "How have you been feeling since I saw you last?" Study staff will also review the previous AE form and inquire whether any of those events are continuing. Study clinicians will follow all AEs, regardless of severity, until resolution or until four weeks following completion of the trial. Each new or unresolved AE will be recorded on the AE case report form according to standard procedures. All AEs will be assigned a severity (mild, moderate, severe or life-threatening), as defined by the DAIDS Table for Grading Severity of Adult Adverse Experiences for HIV Prevention Trials.¹⁴⁸ The study clinician will review the information and offer an educated opinion about the relatedness of the event to the study drug. These data will be reviewed by the PI or Co-Investigator on a weekly basis.

A summary report of all AEs (including SAEs) will be prepared at least every six months (frequency determined by our IRB, DSMB, and NIH), to be submitted to the DSMB, IRB and NIH. SAEs are defined as any fatal event, any immediately life-threatening event, any permanent or substantially disabling event, any event that requires or prolongs inpatient hospitalization, or any congenital anomaly. This category also includes any other important medical event that a study investigator judges to be serious because it may jeopardize the subject or require intervention to prevent one of the above reportable outcomes, or which would suggest a significant hazard, contraindication, side effect, or precaution. An unexpected event is one that is not described with respect to nature, severity, or frequency in the current protocol, investigator's brochure, or product labeling. All AEs that are both serious and unexpected will be reported to the DSMB and UCSF IRB, in writing, within 10 working days. If the SAE is fatal or life threatening, the PI will notify the FDA by telephone within 24 hours, with a followup written report within two working days.

As required, expedited reporting of SAEs to the NIH will adhere to the following guidelines:

1. Apply regardless of the investigator's assessment of the relatedness of the SAE to the intervention under study;
2. Apply equally to trials requiring an IND and those not requiring an IND;
3. Apply to any SAEs that occur during the post-treatment observation period defined by the protocol; and

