Trial stopping rules: There are no formal trial stopping rules for this study. No formal interim efficacy analysis will be conducted. If it becomes clear that the trial puts undue safety risk on study participants, outcomes are poor, or the trial will not achieve its enrollment goals, consideration will be given to stopping the trial, after consultation with the DSMB, IRB, and NIDA PO. The overall safety risk to study participants will be determined through regular monitoring procedures. Safety issues will be evaluated as they arise; participants are given the pager number of the clinician on call which they can page in the event of an emergency or safety risk. Study clinicians will consult with [name], the Principal Investigator and [name], the medical director, on these safety issues on a case-by-case basis as they are reported by the participant. Non-urgent clinical issues that arise during the course of the study are discussed by the team's research clinicians at the next weekly meeting with the PI [name]. During weekly meetings, study clinicians will review all the safety issues and incident adverse events (including lab abnormalities) for the study overall, by system category, and by possible relationship to the study drug. The PI will alert the DSMB and the NIDA PO immediately if at any point the team observes an unexpected frequency of serious AEs possibly related to kudzu. At that point, the PI will consult with the DSMB to determine if changes to the protocol or consent form are needed, or if additional safety data are needed to evaluate participant safety. The PI will consult the DSMB to determine if the trial should be stopped after the committee has reviewed available safety data to date.

14.2 * DATA AND SAFETY MONITORING BOARD (DSMB): (REQUIRED) Will a Data and Safety Monitoring Board (DSMB) be established:

Yes
 No

14.3 DSMB DETAILS: Provide details about the DSMB, including meeting frequency, and the affiliations and qualifications of members: **Attach the DSMB charter to the Other Study Documents section. If the DSMB has not yet been established, submit details and the charter to us as soon as they become available.**

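### The immediate alert on serious adverse events in Protocol section 14.1 names kudzu, a product that no participant in this trial receives

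*Protocol*

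**What the plan says.** Section 14.1 of the Protocol, under Trial stopping rules, states that the trial has no formal stopping rules and no formal interim efficacy analysis. It then describes weekly meetings at which study clinicians review adverse events, including by their possible relationship to the study drug. The next sentence sets a trigger: the principal investigator is to alert the DSMB and the NIDA program officer immediately on an "unexpected frequency of serious AEs possibly related to kudzu". Consultation with the DSMB on possible changes to the protocol or consent form follows.

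The treatments are described elsewhere. Under section 8.3, participants will "receive 12 weeks of as-needed intermittent oral naltrexone 50 mg enhanced with an EMA-informed EMI platform, or receive as-needed placebo with EMA-informed EMI". Section 11.1 gives the split: "40 participants will receive Intermittent Oral Naltrexone and 20 participants will receive placebo". The drug entry in section 10.2 is "NALTREXONE HYDROCHLORIDE" and nothing else. Kudzu appears in Table 1 of section 8.5, in the row for the "Harness Study (Intermittent Oral Kudzu"), one of the team's other trials. The SAP mentions neither kudzu nor safety alerts.

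**The concern.** The alert depends on a causal judgement about a named product, and that product is in neither arm. Applied as written, the condition cannot be met by any event attributed to naltrexone or to the blinded capsule.

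The wording matters because section 14.1 sets no formal stopping rules. This sentence is the Protocol's explicit, immediate trigger on how often serious events occur across the trial. Section 13.2 already describes serious risks of naltrexone taken with opioids, including severe withdrawal and, with large amounts of opiates, overdose, coma or death. It also warns that fentanyl may be present in street methamphetamine. Because such events are described in advance, a single case might be judged expected in nature. A clearly worded alert on frequency is useful for exactly those events.

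**Working it through.** The plan gives no figure on this point, so the check compares wording, with one simple count.

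**1. Product in the rule.** Section 14.1, Trial stopping rules: kudzu.

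**2. Products participants receive.** Section 8.3: naltrexone 50 mg or placebo, both with the momentary intervention. Table 4 (section 8.11): the arm variable has the same two levels. Section 11.1: 40 + 20 = 60, which is the whole enrolment target, so there is no third group. Section 10.2: naltrexone hydrochloride only.

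**3. Mentions of kudzu.** There are two in the Protocol and none in the SAP. One is this rule. The other is Table 1, where kudzu belongs to an ongoing study of 120 people.

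**4. Could kudzu enter by another door?** Exclusion criterion 7 in section 11.8 bars people currently in another intervention study with potential overlap, so the rule is not plausibly about co-enrolled participants.

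**5. Two readings.** Literally, the alert never applies in this trial. In context, the sentence before it uses *study drug* and the sentence after it concerns this trial's protocol and consent form, so *study drug* is the evident meaning and the effect is nil.

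**6. What remains on the literal reading.** These routes name no product:

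| Place | Trigger | To whom | Timing |
|---|---|---|---|
| 13.3 | Serious or unexpected events | DSMB, IRB, NIH, FDA as required | Specified time frames |
| 14.1, AE Reporting | Events both serious and unexpected | DSMB, IRB | 10 working days |
| 14.1, AE Reporting | Fatal or life-threatening events | FDA | 24 hours by telephone |
| 14.1, AE Reporting | Serious events, whatever their relatedness | NIH | Expedited; no deadline given there |
| 14.1, AE Reporting | Summary of all events | DSMB, IRB, NIH | At least every six months |
| 14.1, Reporting of other study events | Major change in protocol status; the list ends in a catch-all | NIH program officer, DSMB | Immediate |
| 14.1, Trial stopping rules | Undue safety risk | DSMB, IRB, NIDA program officer consulted | None stated |
| 14.1, closing sentence on stopping | Whether to stop the trial | DSMB consulted | None stated |
| 14.3 | As-needed meetings | DSMB | As needed |

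By place, in table order: 1 + 4 + 1 + 2 + 1 = 9 routes. Clearly an immediate alert to both the DSMB and the NIDA program officer on aggregate serious-event frequency: 0 of 9. Arguably so: 1 of 9, the notice under Reporting of other study events. That notice has the same two recipients and the same immediacy, but its opening words concern changes in protocol status, so whether it covers a cluster of serious events is open to dispute.

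**The case against.** The strongest reply is that nobody would be misled. A literal reading gives a rule that could never operate, the neighbouring sentences point to the study drug, and a reasonable investigator would apply it that way. That is fair, and it is why the point is minor.

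Oversight of event frequency also does not rest on this sentence alone. Section 14.1 defines an unexpected event with reference to nature, severity or frequency. A serious event occurring unusually often could therefore itself count as unexpected, and the Protocol says: "All AEs that are both serious and unexpected will be reported to the DSMB and UCSF IRB, in writing, within 10 working days". Section 13.3 adds: "If serious or unexpected AEs occur during the trial, the PI will report these occurrences within the specified time frames". There is a scheduled aggregate view as well: "A summary report of all AEs (including SAEs) will be prepared at least every six months". Section 14.3 has DSMB clinicians reviewing reported events and a statistician reviewing the data periodically for emerging problems. All of this stands as mitigation. However, the 10-working-day report is not immediate and does not name the NIDA program officer.

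Two cautions about the table also stand. What counts as a separate route is partly a matter of judgement: the closing sentence on stopping, for example, can be read as following from the kudzu trigger. Nine is therefore a convenient tally, not a measurement. The DSMB charter and the DSMB information sheet, to which section 14.3 refers, were not supplied and may contain further escalation rules. Neither caution changes the fact that the rule names the wrong product.

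**Conclusion.** The concern holds. The rule is wrong as written, with high confidence, and the severity is minor. It is a wording error, not a design choice: the documents give no reason for naming kudzu. Text carried over from the team's kudzu study is the likely source, but that is an inference from Table 1 and the conclusion does not depend on it.

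No delay, risk figure or statistical consequence is claimed. If the team reads the word as the study drug, the effect is nil. If the sentence is applied literally, the trial loses its one clearly stated immediate alert on the frequency of serious events, while the slower or differently triggered routes remain. The consultation with the DSMB that follows the alert is not clearly lost, because other clauses also call for it. The conclusion rests on the supplied Protocol and SAP only.

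**What to change.** In section 14.1, Trial stopping rules, replace *kudzu* with *the study drug (naltrexone or placebo)* and leave the rest of the rule unchanged. The parenthesis is optional: *the study drug* alone would match the preceding sentence. Either form suits a double-blind trial, in which staff cannot attribute an event by arm.

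The cost is a minor IRB-approved amendment, with notice to the NIH program officer and the DSMB because section 14.1 lists protocol amendments among the changes to be notified. That burden is small but not nil. Endpoints, analyses, sample size and the SAP are untouched.

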15.0 Confidentiality, Privacy, and Data Security

15.1 PROTECTING PRIVACY: Indicate how subject privacy will be protected:

- Conduct conversations about the research in a private room
- Ask the subject how they wish to be communicated with – what phone numbers can be called, can messages be left, can they receive mail about the study at home, etc.
- Take special measures to ensure that data collected about sensitive issues do not get added to their medical records or shared with others without the subject's permission
- Other methods (describe below)

15.2 SENSITIVE DATA: Do any of the instruments ask about illegal or stigmatized behavior:

Yes No

IMPORTANT NOTE: Indicate in the consent form what kinds of sensitive information will be collected.

15.3 SIGNIFICANT CONSEQUENCES OF A LOSS OF PRIVACY OR CONFIDENTIALITY: Could a breach of privacy or confidentiality result in any significant consequences to participants, such as criminal or civil liability, loss of state or federal benefits, or be damaging to the participant's financial standing, employability, or reputation:

Yes No

Check all that apply:

- Embarrassment
- Criminal or civil liability
- Loss of state or federal benefits
- Damaging to the participant's financial standing, employability, or reputation
- Potential risks to insurability (health, disability, or life insurance)

Describe the potential consequences:

Other potential risks to participating in this study include: unauthorized disclosure of confidential information; discomfort or embarrassment related to specimen collection or questionnaires dealing with personal habits and lifestyle, including drug or alcohol use; and possible unwanted encounters with friends or associates in the research setting.

15.4 EXTRA CONFIDENTIALITY MEASURES: Explain any extra steps that will be taken to assure confidentiality and protect identifiable information from improper use and disclosure, if any:

The study consent form will inform participants of confidentiality guidelines. Strict confidentiality will be maintained. Records that have personal identifiers (e.g., clinical records) will be stored in a locked

cabinet separate from the research record, which will contain only the participant's ID number. Only the research team and clinical staff assigned to the care of the participants will have access to non-anonymous records. All research data are maintained in binders in locked cabinets. Consent forms, which contain names, are stored separately. Enrollment and randomization ID numbers are used to identify specific research forms. Files that link participants' name with enrollment and randomization ID numbers will be kept in a locked file. No presentation or publication of the study results will refer to participants individually. Prior to any sharing of the research dataset, all personal identifiers will be removed. Data will be shared only with researchers who have received IRB-approval for their studies, and who agree not to identify any specific study participant in any way, and who will destroy or return the dataset after completing their analyses.

The study will follow HIPAA regulations for the protection of private health information for individuals. All study participants enrolled or enrolling in our studies must sign the HIPAA Authorization Form. The Authorization Form is protocol-specific and must be signed along with the consent form when participants first screen or enroll into a study. Before participants sign the Authorization Form, study staff will explain the purpose of the Authorization Form and answer any of the participants' questions. Participants will receive a signed copy of the Authorization Form. Potential participants who choose not to sign the HIPAA Authorization form will be excluded from study participation.

For the safety to participants and staff during COVID-19, the study has been designed with hybrid visits according to Interim UCSF research guidelines. The weekly visits (weeks 1, 2, 3, 5, 6, 7, 9, 10 and 11) will be conducted remotely through zoom. The participant will be given single M-AMP urine test kits and urine collection bottles at the in-office visits and trained how to conduct the urine test. The participant is asked to provide a urine sample in the urine collection bottle before the video visit. The participant will dip the M-AMP stick in the urine during the video visit and the dip stick will be shown to the counselor. Due to video resolution, a faint red line may not be able to be viewed by video. If this happens, the participant will be asked to take a picture of the dip stick and upload it to a secure portal or an encrypted e-mail. After IRB approval, we will test this option on RedCAP through the participant survey invitation and embedded image upload option.

15.5 * REPORTABILITY: Do you anticipate that this study may collect information that State or Federal law requires to be reported to other officials, such as elder abuse, child abuse, or threat to self or others: (REQUIRED)

Yes No

The confidentiality and privacy section of the consent form should include this as a possible risk of participation.

*** Describe the types of reportable information the research team may encounter and provide the details of the reporting plan: (REQUIRED)**

Exceptions to confidentiality for participants are those required by law such as a diagnosis of sexually transmitted infections (STIs) including HIV, CD4 and Viral Load and threat of imminent action on suicidal or homicidal ideation. At any time, persons judged by project investigators to be a danger to self or others, will be escorted to San Francisco General Hospital. All staff, including research assistants and counselors, receive yearly training for identifying suicide /homicide risk and/or dangerous intoxication, and de-escalation of agitated or angry persons. All staff are trained to appropriately respond to these situations by immediately contacting a study clinician to evaluate the participant.

15.6 CERTIFICATE OF CONFIDENTIALITY: Will this study obtain a Certificate of Confidentiality:

Yes No

Please include the recommended Certificate of Confidentiality language in the consent form.

15.7 SHARING OF RESEARCH RESULTS: Will there be any sharing of **EXPERIMENTAL research test results with subjects or their care providers:**

Yes No

15.9 * HIPAA APPLICABILITY: Study data will be: **(REQUIRED)**

- Derived from a medical record (e.g. APeX, OnCore, etc. Identify source below)
- Added to the hospital or clinical medical record
- Created or collected as part of health care
- Used to make health care decisions
- Obtained from the subject, including interviews, questionnaires
- Obtained ONLY from a foreign country or countries
- Obtained ONLY from records open to the public
- Obtained from existing research records
- None of the above
- Derived from the Integrated Data Repository (IDR) or The Health Record Data Service (THREDS) at SFGH

In addition to signing a consent form, each subject will have to sign the UCSF Research Subject Authorization Form (HIPAA Form).

Upload the HIPAA Authorization Form in the Other Study Documents section of the Initial Review Submission Packet Form. Failure to have patients sign the HIPAA Authorization is one of the most common findings from QIU Routine Site Visits. Please call the IRB office at [contact] if you have questions about HIPAA research requirements.

If derived from a medical record, identify source:

Clarifying health data may be requested from PCP, inpatient and/or ED visits.

15.10 * IDENTIFIERS: Check all identifiers that will be collected and included in the research records, even temporarily: **(REQUIRED)**

- Names
- Dates
- Postal addresses (if only requesting/receiving zip codes check Yes to the Zip Code question below instead of checking this box)
- Phone numbers
- Fax numbers
- Email addresses
- Social Security Numbers*
- Medical record numbers
- Health plan numbers
- Account numbers

- License or certificate numbers
- Vehicle ID numbers
- Device identifiers or serial numbers
- Web URLs
- IP address numbers
- Biometric identifiers
- Facial photos or other identifiable images
- Any other unique identifier
- None

* Could study records include ANY photos or images (even 'unidentifiable' ones): **(REQUIRED)**

Yes No

* Please provide a justification for including the Social Security Number (SSN) in your data set. Best practices dictate that you store the SSN separately from the full data set in a password protected file. **(REQUIRED)**

California regulations require that positive HIV test results be reported to the county public health department, even if it is not a new diagnosis for the individual. HIV test result reporting includes CD4+ count (or T-cell count), viral load, and viral genotype for positive results. This information is used to track the disease statewide and nationwide.

The report includes details like participant name, social security number, and other identifying information. The San Francisco Department of Public health may share the results with the participant's home county health department if they do not live in San Francisco County. Other than this required reporting, test results will be treated confidentially by the study staff and personally identifying information will not be reported to other departments or agencies.

15.12 * PATIENT RECORDS: Will health information or other clinical data be accessed from UCSF Health, Benioff Children's Hospital Oakland, or Zuckerberg San Francisco General (ZSFG): (REQUIRED)

Yes No

15.15 * HIPAA - PERMISSION TO ACCESS SENSITIVE DATA: Does the research require access to any of the following types of health information from the medical record: (check all that apply) (REQUIRED)

- Drug or alcohol abuse, diagnosis or treatment
- HIV/AIDS testing information
- Genetic testing information
- Mental health diagnosis or treatment
- None of the above

Important note: Ensure that participants initial the corresponding line(s) in Section C of the HIPAA authorization form during the consent process.

15.19 * DATA COLLECTION AND STORAGE: (check all that apply): (REQUIRED)

Collection methods:

- Electronic case report form systems (eCRFs), such as OnCore or sponsor-provided clinical trial

management portal

- UCSF ITS approved Web-based online survey tools: Qualtrics or RedCap
- Other web-based online surveys or computer-assisted interview tool
- Mobile applications (mobile or tablet-based)
- Text Messaging
- Wearable devices
- Audio/video recordings
- Photographs
- Paper-based (surveys, logs, diaries, etc.)
- Other:

* Specify what other methods will you use to collect data: **(REQUIRED)**

If the counselor is unable to read the urine dip stick through the remote video visit, the participant will be asked to take a photo of the dip stick result and upload this to a secure portal or encrypted e-mail.

* What online survey or computer assisted interview tool will you use: **(REQUIRED)**

- Qualtrics (Recommended)
- RedCAP (Recommended)
- Survey Monkey (NOT recommended and may require UCSF ITS Security review)
- Other

* What's the name of the survey tool and who is it owned by: **(REQUIRED)**

We will use PiLR Health's Ecological Momentary Assessments (EMA) messages for the Ecological Momentary Interventions (EMI). To collect self-adherence measures we will use MEMs caps which we have used in previous studies.

If the survey tool is not provided by the study sponsor, and the survey tool stores data on a server, vendor, cloud, or 3rd party, contact [contact] to determine if you need to complete a security assessment.

* Data will be collected/stored in systems owned by (check all that apply): **(REQUIRED)**

- Study sponsor
- UCSF data center (including OnCore, RedCap, Qualtrics, and MyResearch)
- UCSF encrypted server, workstation, or laptop residing outside of UCSF data center
- Personal devices, such as laptops or tablets that are not owned or managed by UCSF
- SF VAMC
- Zuckerberg San Francisco General Hospital
- Benioff Children's Hospital Oakland
- Langley Porter Psychiatric Institution
- Other UCSF affiliate clinic or location (specify below)
- Cloud vendor such as Amazon Web Services (AWS), Salesforce, etc. (specify below)
- Other academic institution
- 3rd party vendor (business entity)
- Other (explain below)

* Provide more details about where study data will be stored: **(REQUIRED)**

All data collected will be collected and stored at the San Francisco Dept of Public Health office on [name]. Records that have personal identifiers (e.g., clinical records) will be stored in a locked cabinet separate from the research record, which will contain only the participant's ID number. Only the

research

team and clinical staff assigned to the care of the participants will have access to non-anonymous records.

All research data are maintained in binders in locked cabinets. Consent forms, which contain names, are stored separately.

Enrollment and randomization ID numbers are used to identify specific research forms. Files that link participants' name with enrollment and randomization ID numbers will be kept in a locked file in a locked room.

Information collected through ecological momentary intervention messages will be stored only for the duration of the study. No sensitive information is collected. PiLR Health is also a HIPAA compliant system.

15.20 * ADDITION OF RECORDS TO A REGISTRY: Will patient records reviewed under this approval be added to a research database, repository, or registry (either already existing or established under this protocol): (REQUIRED)

Yes No

15.21 * DATA SHARING: During the lifecycle of data collection, transmission, and storage, will identifiable information be shared with or be accessible to anyone outside of UCSF: (REQUIRED)

Yes No

